Additional, well-controlled studies are needed to understand and advance our knowledge regarding the effect of the A118G SNP and additional OPRM1 tagging SNP variants on baseline pain tolerance, and pain tolerance under conditions of opioid analgesic treatment. Only two studies have examined the contribution of the A118G on pain tolerance in controlled laboratory settings (78, 81). The first study reported positive associations between A118G and pain on two of the three pain tolerance tests conducted, but did not evaluate tolerance to pain following opioid agonist administration (78, 81). The second study reported a positive association with OPRM1 on one test of pain following oxycodone administration, but did not evaluate additional pain tolerance tests, which is important given the high rate of individual variability among pain testing methods (78, 81). Neither study sampled across the OPRM1 gene and or was designed to prospectively evaluate gender, which is critical because of the robust gender-specific effect that exists on pain and its potential interaction with the OPRM1 gene (41). The current study will extend upon these studies by evaluating the effect of the A118G SNP and OPRM1 gene using a quantitative sensory testing (QST) paradigm, under conditions of double-blind and placebo-controlled hydromorphone administration, and will conduct gender specific analyses. Women will only be enrolled during the first two weeks of their cycle (confirmed via progesterone analysis) to minimize hormonal effects on pain, which will be the most rigorous evaluation of OPRM1 and pain within gender to date. Further, one of our pain tests will activate the diffuse noxious inhibitory control (DNIC) system, which is mediated by the endogenous opioid system, hypothesized to be a model of chronic pain, and believed to contribute to opioid-induced hyperalgesia (97). No prior study has used the DNIC procedure to evaluate OPRM1 effects on pain tolerance, which is critical because of the established functional relationship between the OPRM1 and the endogenous opioid response (26, 98). The results will advance our understanding of the OPRM1 contribution to pain tolerance and response to medication, help elucidate the

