#### 4. Study Procedures

- a. Study design, including the sequence and timing of study procedures (distinguish research procedures from those that are part of routine care).

**Study Overview:** This study will be a between-group (total completer N=100) evaluation of genotype and sex, and a within-subject evaluation of opioid dose-response. The study will be conducted over 5 days (4 nights) at the Behavioral Pharmacology Research Unit (BPRU) and a residential clinical research unit (CRU) (Figure 1). Day 1 will be an Admission day. Days 2-5 will consist of blinded study drug administration in the morning, 1 pain testing session, and self-report/physiological measures of drug effects for 6 hours post dosing. Participants will receive double-blind doses of oral hydromorphone (2mg, 4mg, 8mg) (99-102) or weight and color-matched placebo in a randomized, counter-balanced research design.

**Screening Visit:** Participants will complete a brief phone screen to determine initial eligibility and will be invited to complete an in-clinic screen. Participants will sign an informed consent form with a study staff member to begin the Screening visit. To reduce expectancy effects, the consent will inform participants the study drug may consist of one or more of numerous different drug classes (e.g., opioids, stimulants, over-the-counter medications), a common practice in laboratory based studies of drug effects (103, 104). Following consent, a staff member will administer a battery of measures to establish study eligibility (see Study Measures below). A urine sample will be collected and tested for evidence of illicit drugs and to establish medical eligibility. A blood sample of no more than 2 tablespoons will also be collected from eligible participants for medical and genotype analysis. Participants will also be asked to provide a second blood sample (2 additional tablespoons) that will be collected at either Screening or Admission and stored for future genetic analysis. This will be voluntary. Participants who meet eligibility criteria (including results of laboratory blood tests) will be scheduled for an Admission day.

**Study Day 1, Admission Visit:** Participants will complete a brief history and physical to determine final study eligibility and will be admitted to the CRU for 5 days (Admission day + 4 session days). During the Admission day, participants will be familiarized with the pain testing procedures and the measures used during session days 2-5.

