**Association Model:** Our primary goal is to demonstrate the impact of SNP variation across OPRM1 on variability in response to hydromorphone across time and dose. Association analyses will be performed by modeling genotype at each SNP in a general linear model. In its simplest form this test, commonly termed the measured genotype analysis (137), models the influence of genotypic variation at a given locus on variation in the quantitative trait, essentially a one-way Analysis of Variance (ANOVA). This approach provides a distinct advantage in that it can easily be extended to a two-way ANOVA to model genotype effects across 3 different doses of drug. In addition, the flexibility of the GLM allows incorporation of ancestry covariates and environmental moderators or mediators. We will examine the impact of OPRM1 at each time-point in separate analyses and account for the multiple testing using LD-adjusted Bonferroni correction (see below).

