**Power and Correction for Multiple Testing:** Power (1-Type II error) and correction for multiple testing (control of Type I error) are important considerations in any genetic association study. Typically investigators attempt to control the Type I error rate of a given set of hypothesis tests by controlling the family wise error rate through manipulation of the alpha level of the test. This is not problematic when a handful of tests are performed at an alpha level (false positive level) of 5%, where the usual approach is the Bonferroni correction. We anticipate performing tests across multiple time-points and must adjust our target alpha level. Importantly, our 71 selected SNPs across the OPRM1 gene (see below) do not represent 71 independent tests due to correlation between SNPs. We will use an approach, termed SNPSpD (138) which uses spectral decomposition to estimate the number of independent tests across the region. Using available HapMap data, we estimate 44 independent tests across the region. We calculate power for the GLM approach modeling the effect of genotype on phenotype. If we assume a constant effect size difference between genotype groups (at each dose other than placebo), at an alpha level conservatively adjusted for 50 tests to .001, using the entire completer sample (N= 100) or the sex subsamples (N=50), we have >80% power for modest effect sizes of ~.45 and .67 respectively. In our calculations, effect size (Cohen's d) is the mean difference between genotype groups in standard deviation units. Importantly, this effect size is well within the range seen by other studies examining drug response difference in OPRM1 (e.g., Ray et al., 2004: effect size = 1.2).

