**Analysis of pain testing sessions:** We hypothesize that OPRM1 SNP variants will exhibit greater pressure pain thresholds, greater CPM efficiency, lower hydromorphone-related analgesia, and lower cortisol stress response than participants with the major allele, and that results will be positively correlated with response to self-report and physiologically-mediated hydromorphone drug effects collected during days 3-5. Pressure pain threshold will be estimated by averaging the results of the 2 administrations to radiobrachialis and quadriceps muscle groups. We will generate a CPM index for each participant [(mean pressure pain threshold during cold pressor)/(mean pressure pain threshold prior to cold pressor)] x 100 (90). These values will provide a quantitative measure of percent change in the test stimulus (i.e., pressure point threshold). Mixed effects regression models with a random intercept will be used to compare dependent variables (pressure pain threshold, DNIC threshold, DNIC index) as a function of within-subject drug effects (placebo vs. hydromorphone), and between-subject effects of OPRM1 SNP analysis will be conducted as specified in Aim 1. Gender, age, and race have been associated with response to pain and the CPM test (146-148). Gender will be evaluated using independent subgroup analyses and age and race will be included as covariates. Finally, subscale scores of self-report measures of pain and coping strategies will be compared between the two genotype groups using independent samples t-tests, and drug identification data will be compared using a chi-square for each drug condition. We expect that both experimental manipulations will induce pain in the minor and major allele groups, and that participants with the minor allele will demonstrate lower sensitivity to pain (e.g., greater pressure pain magnitudes), lower NRS ratings of pain, lower cortisol response to painful stimuli, and lower analgesic relief from hydromorphone compared to the major allele participants.

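### The pain analysis names sex as a correlate of the outcome but adjusts only for age and race, so a pooled genotype model fitted as written gives up some precision

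*Combined protocol and SAP*

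**What the plan says.** Section 4a describes the study as a "between-group (total completer N=100) evaluation of genotype and sex, and a within-subject evaluation of opioid dose-response", so sex stands beside genotype as a between-person factor. Section 3 (Background) refers to a "robust gender-specific effect that exists on pain".

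In section 7c, Analysis of pain testing sessions, the plan states that "Gender, age, and race have been associated with response to pain and the CPM test". Its rule for handling the three is: "Gender will be evaluated using independent subgroup analyses and age and race will be included as covariates". The pain outcomes go into mixed models with a random intercept, and the SNP effects follow the Aim 1 method.

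That method is in section 7c, Association Model. It says the general linear model permits "incorporation of ancestry covariates and environmental moderators or mediators". Sex is not named.

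Section 7c, Power and Correction for Multiple Testing, computes power "using the entire completer sample (N= 100) or the sex subsamples (N=50"), which shows that a pooled genotype test is planned as well as within-sex tests.

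**The concern.** Three factors are named as related to the pain outcomes, and two become covariates. The third is the one called robust elsewhere in the protocol, and no reason is given for treating it differently.

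Analyses within each sex do not help the pooled test. If 100 people are analysed together without a sex term, the difference between men and women stays in the between-person error against which the genotype main effect is judged. Pain threshold is listed among the primary outcomes in section 7a, and its genotype comparison is between persons. At stake is the standard error of that comparison at a strict alpha of .001.

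**Working it through.** **The plan's own power figure.** The plan states its power "at an alpha level conservatively adjusted for 50 tests to .001" and reports "we have >80% power for modest effect sizes of ~.45 and .67 respectively". Sidedness, carrier share and within-person correlation are not stated. With equal genotype groups, one value per person and a two-sided test:

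- N=100: 0.45 × √100 / 2 = 2.25, and Φ(2.25 − 3.29) = 14.9% (13.5% by noncentral t).
- N=50: 0.67 × √50 / 2 = 2.37, and Φ(2.37 − 3.29) = 17.8%.
- Three active doses treated as independent values: 0.45 × √300 / 2 = 3.90, and Φ(3.90 − 3.29) = 72.8% for N=100. The same approach gives 79.2% for N=50. One-sided, the two are 79.0% and 84.4%.

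The stated 80% is therefore not reproduced and cannot serve as the baseline here. That is a separate and larger issue. The gain from adjustment is best given as a ratio of precision, which does not depend on it.

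**Gain from a sex term.** Let ds be the sex difference in within-sex SD of the value that enters the test. The documents give no size, so a range is assumed. Equal numbers of each sex are inferred from the N=50 subsamples. The plan's d is taken on the total SD, a point the documents leave open.

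- Share of between-person variance due to sex: R² = (ds²/4) / (1 + ds²/4).
- Adding sex multiplies the error SD by √(1 − R²).
- Equivalent sample size: 100 / (1 − R²) = 100 × (1 + ds²/4).

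| ds | R² | SD ratio | Worth, instead of 100 | Power, one value per person (13.5% unadjusted) | Power, three independent doses (72.8% unadjusted) |
|---|---|---|---|---|---|
| 0.2 | 1.0% | 0.995 | 101 | 13.7% | 73.4% |
| 0.5 | 5.9% | 0.970 | 106 | 15.0% | 76.6% |
| 0.8 | 13.8% | 0.928 | 116 | 17.5% | 81.8% |
| 1.0 | 20.0% | 0.894 | 125 | 19.9% | 85.7% |

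The last column is only an illustration. Zero within-person correlation is not stated in the plan, and a sex difference carried through all of a person's sessions would itself correlate them.

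**Which contrasts are affected.** A simulation used 4,000 runs, N=100, placebo plus three active doses, and an assumed between-person SD of 0.8 and residual SD of 0.6.

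- Genotype main effect, sex difference 0.8: SE 0.190 without sex and 0.172 with it (power 89.7% and 95.5% for the simulated effect).
- Genotype main effect, sex difference 0.5: SE 0.179 and 0.172 (power 95.3% and 96.8%).
- Genotype-by-drug contrast: SE 0.139 without sex and 0.140 with it. Each person is their own control, so a sex main effect cancels.
- No genotype effect, alpha .05: rejection stays near 5% with or without sex.

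The simulated ratio at 0.8 is (0.190/0.172)² = 1.22, not 1.16, because averaging four sessions shrinks the within-sex variance to 0.8² + 0.6²/4 = 0.73, and 1 + (0.8²/4)/0.73 = 1.22.

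**Chance imbalance in sex between genotype groups.** Take 20 carriers and 80 non-carriers (assumed) and ds = 0.8.

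- Adjusted SE: √(1/20 + 1/80) = 0.25.
- SD of the imbalance in proportion female: √(0.25 × (1/20 + 1/80)) = 0.125, which moves the estimate by 0.8 × 0.125 = 0.10.
- Combined: √(0.25² + 0.10²) = 0.269 = 0.25 × √1.16, the unadjusted SE.

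The imbalance is exactly the variance already counted in the table.

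**The case against.** The strongest reply is that no sentence excludes sex from a pooled model. Section 4a makes sex a study factor, section 7b lists its effect on all outcomes as a secondary outcome, and the Association Model leaves covariates open. The pain paragraph does not say whether genotype is tested pooled, within sex, or both. Tests run only within sex would have no between-sex variance in their error. This stands as a limit: the omission is read from the stated covariate rule and from silence. It does not dispose of the point, because the power paragraph relies on a pooled N=100 test and the one sentence that commits to a treatment of gender does not make it a covariate.

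A second reply is that the benefit may be trivial. That also stands: at 0.2 SD it is worth about one participant in 100.

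A third is that the robust effect is claimed for pain, and the association for pain and CPM. Nothing in the documents gives a sex effect on high, liking, pupil diameter or blood pressure. So for Aim 1 the case for adjustment is consistency, not documented gain.

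A reader might also infer that leaving sex out biases the genotype estimate or inflates type I error, with chance imbalance as a second harm. The documents do not support this. Nothing in them links genotype to sex, and under independence the imbalance is part of the same random error.

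**Conclusion.** The point holds as one of precision. The plan's covariate rule, applied to the pooled N=100 pain models, leaves between-sex variance in the between-person error of the genotype main effect. Adjustment is worth about 101 to 125 participants instead of 100 for sex differences of 0.2 to 1.0 within-sex SD. Where the true value lies cannot be settled from the documents.

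This rests on three assumptions: roughly equal numbers of each sex, genotype independent of sex, and a pooled model fitted as written. A reader might take the 50/50 split as a recruitment quota, but only the subsample size in the power paragraph implies it. A reader might also add the gain to the claimed 80% power; since that figure is not reproduced, gains in percentage points counted from it are not reliable. Drug-minus-placebo contrasts, including analgesic efficacy, are not improved by a sex main effect.

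**What to change.** In section 7c, Analysis of pain testing sessions, state that the pooled (N=100) genotype models for the pain outcomes include sex as a fixed covariate together with age and race. For consistency, say in the Association Model paragraph that the pooled Aim 1 models include sex together with ancestry. Keep the within-sex analyses as planned.

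The cost is a sentence in each paragraph and one degree of freedom per model, with no new data. Setting it down in advance also removes a later choice between adjusted and unadjusted results.

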
#### 2. Objectives (include all primary and secondary objectives).

The primary aim of this study is to examine the associations of specific polymorphisms in the OPRM1 gene with mu opioid receptor (MOR)-mediated effects. We hypothesize the minor A118G SNP allele and OPRM1 tagging SNPs will predict more reinforcing properties of hydromorphone, (e.g., higher self-report ratings of high and drug-liking) and greater opioid-induced physiological changes (e.g., pupil diameter, blood pressure), decreases in cortisol levels as a function of the degree of pleasant effects of hydromorphone, and steeper discounting curves on a delay-discounting task. The secondary aim of this study is to examine the associations of specific polymorphisms in the OPRM1 gene with laboratory measures of pain. We hypothesize the minor A118G SNP allele and OPRM1 tagging

SNPs will predict higher pain threshold on two experimentally-induced laboratory measures of pain, lower analgesic efficacy in response to experimentally-induced pain, and lower cortisol response to painful stimuli. Finally, as an exploratory aim, we will examine the contribution of sex to the primary and secondary aims.

**3. Background** (briefly describe pre-clinical and clinical data, current experience with procedures, drug or device, and any other relevant information to justify the research)

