**d. Early stopping rules.** The safety of participants is a priority of BPRU. If a participant experiences a serious side effect that seems to be related to the study drug, s/he will be discontinued from the study. If clinically indicated the participant will be referred to the Johns Hopkins Bayview Medical Center (JHBMC) Emergency Department for further treatment. BPRU and the CRU have policies in place to ensure safety of all participants and staff, and some policies may lead to administrative discharge of a participant, and therefore, discontinuation from the study. Participants who do not abide by the BPRU policies and procedures, or who demonstrate behaviors abusive of staff or other participants may be discontinued from the study. Intercurrent illness or condition changing a participant risk may result in medical discharge from the study.

Stopping criteria for the study: In addition, an independent panel of consultants will be contracted for review of the risks-benefits ratio of the study. At mid-point during enrollment this panel will be provided with a report of adverse events and participant outcome data (subjective response to hydromorphone) by unlabeled sex groups (A vs. B). This information will be used to assess whether the risks reported are considered to be of unusual magnitude or frequency across any specific group, and to determine whether the study should be ended prematurely due to participant safety concerns or because a result has been unequivocally demonstrated. It is unlikely that such a small study would be interrupted because of a large rate of adverse events, particularly given the noninvasive administration method of the medication (i.e., oral) and our experience at administering this drug, however we will ensure that a qualified panel of reviewers makes this decision.

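### The mid-enrolment panel may end the study on a demonstrated result, but the outcome data listed for it are split by sex rather than genotype, and no test or boundary is given

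*Combined protocol and SAP*

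**What the plan says.** Section 7d (Early stopping rules) describes one scheduled look by an independent panel: "At mid-point during enrollment this panel will be provided with a report of adverse events and participant outcome data". The outcome part is specified as "participant outcome data (subjective response to hydromorphone) by unlabeled sex groups (A vs. B"). The panel uses the report to judge whether risks are unusual in any group, and then "to determine whether the study should be ended prematurely due to participant safety concerns or because a result has been unequivocally demonstrated". The two grounds are joined by the word or, so the second stands apart from safety.

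Section 2 (Objectives) makes the association of OPRM1 polymorphisms with opioid-mediated effects the primary aim. Sex comes last: "Finally, as an exploratory aim, we will examine the contribution of sex to the primary and secondary aims".

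The heading of section 7c names interim data analysis, but the text under it contains no interim method. Its multiplicity control covers SNPs and time-points. The power statement there is set "at an alpha level conservatively adjusted for 50 tests to .001", "using the entire completer sample (N= 100) or the sex subsamples (N=50"), and concludes "we have >80% power for modest effect sizes of ~.45 and .67 respectively".

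**The concern.** A rule for stopping on a result has to say which result, on which data, and how strong the evidence must be. This one does none of these.

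- **Contrast.** The primary question concerns genotype, and no genotype grouping is listed for the panel. The only between-group result visible in the listed data is a sex difference.
- **Outcomes.** Section 7a also names pupil diameter, blood pressure, pain threshold and analgesic efficacy as primary variables. The panel's outcome data are described only as subjective response.
- **Criterion.** No hypothesis, test, threshold or boundary defines what counts as demonstrated.

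If the clause were used, the genotype aim would be left at roughly half its planned size because of data that cannot speak to it. The sex-specific genotype analyses, planned on 50 per sex, would be left with about 25 per sex. The protocol gives no power for that size.

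**Working it through.** **Inputs from section 7c.** N=100 completers, or 50 per sex subsample. Alpha = .05/50 = .001. Stated detectable effects are about .45 and .67. A prior study is cited with an effect size of 1.2. The definition is that "effect size (Cohen's d) is the mean difference between genotype groups in standard deviation units".

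**Assumptions not in the documents.** Tests are two-sided. The genotype split is 1:1, with 20% carriers as a sensitivity case. The mid-point is taken as 50 completers.

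**The plan's own power figure.** For two groups, the noncentrality is δ = d / √(1/n₁ + 1/n₂), and power is P(|T| > t crit) for a noncentral t with N−2 degrees of freedom.

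- N=100, d=.45: δ = .45/.200 = 2.25, t crit = 3.393, power 13.5%.
- N=50, d=.67: δ = .67/.2828 = 2.37, t crit = 3.505, power 14.6%.

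The stated power above 80% is not reproduced when the effect is Cohen's d as defined. The figures do fit Cohen's f: 86% and 88% with two genotype groups, 77% and 79% with three. That is a separate problem in section 7c. The present point does not depend on it, since halving N lowers power under either reading.

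**Effect of stopping at half size, in the plan's own terms.** The N=50 figure was written for a sex subsample, but the calculation depends on N alone, so it also describes a pooled sample of 50. The detectable effect rises from about .45 to about .67, a factor of .67/.45 = 1.49.

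**Effect of stopping at half size, recomputed at alpha .001.**

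| Effect and split | δ, N=100 | Power, N=100 | δ, N=50 | Power, N=50 |
|---|---|---|---|---|
| d=.45, 1:1 | 2.25 | 13.5% | 1.59 | 3.7% |
| d=.85, 1:1 | 4.25 | 80% | 3.01 | 33% |
| d=1.2, 1:1 | 6.00 | 99% | 4.24 | 76% |
| d=.85, 20% carriers | 3.40 | 51% | 2.40 | 15% |

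The .45 and 1.2 come from section 7c. The .85 does not appear in the documents; it is the d that N=100 with equal groups detects with 80% power. If .45 is read as Cohen's f, power falls from 86% to 39% with two groups and from 77% to 27% with three.

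**Type I error.** Two unadjusted looks at the same contrast, at half and full information, have correlation √.5 = .707. At a nominal .05, P(|Z₁| > 1.96 or |Z₂| > 1.96) = 8.3%. This applies only to a contrast tested at both looks. On the listed data that could be sex; it is not genotype.

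**The case against.** A reader might infer that an unadjusted mid-point look inflates the false-positive rate of the genotype tests. The documents do not support that. No genotype grouping is listed for the panel, so no genotype alpha is spent and the final genotype level needs no adjustment for this look. The .001 level belongs to the SNP tests and should not be carried over to the panel's look at sex.

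A reader might also take the fall from 80% to 33% as the size of the harm. It rests on an effect chosen to give 80% power at full size. Across the three 1:1 cases the loss runs from about 10 points (13.5 − 3.7) to 47 points (80 − 33). Power falls in every case, but no single figure is established.

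Nor does the plan direct a stop on a sex difference. It permits one. An independent, qualified panel may well decline to treat an exploratory contrast as the study's result, and unequivocal is a demanding word. That objection stands as to likelihood. It does not supply a criterion, because judgement cannot establish a genotype result from data not split by genotype. The protocol's remark that interruption is unlikely refers to adverse events, so it does not limit the second ground.

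Two smaller reservations also stand. The text lists sex groups without saying that nothing else will be shown. And it places the look at the middle of enrolment, not at 50 completers.

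**Conclusion.** The concern holds as a mismatch between a stopping ground and the data listed for it. The panel may end the study on a demonstrated result, but what it is listed to receive cannot demonstrate the primary one, and no test or boundary fills the gap. If the clause were invoked, the cost would be lost power for the genotype aim: a detectable effect of about .67 instead of .45 on the protocol's own figures, or the recomputed losses tabulated above. Those sizes assume about 50 completers at the mid-point, two-sided tests and the stated genotype splits. Inflation to about 8.3% at a nominal .05 would concern only a contrast tested at both looks, here sex. The defect matters only if the clause is used, but it is cheap to remove and should be corrected.

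**What to change.** In section 7d, delete the second stopping ground, that is, everything from the word or to the end of the clause quoted from that section. State that the mid-point review is for safety only and that enrolment continues to 100 completers unless stopped for safety.

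This is about one sentence of wording. It removes no participant protection: the adverse-event report to the panel stays, as does the annual adverse-event review in section 8b. The sponsor gives up an outcome-based stop that the listed data could not support.

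A group-sequential rule on genotype is possible but should not be the main recommendation. The genotype question spans 71 SNPs, several time-points and several outcomes, so the sponsor would first have to name one contrast and one endpoint, arrange for the panel to see data by genotype, and then set a boundary and adjust the final analysis. That is a redesign of the interim plan, not a wording change.
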